#### 8.1.3 Assessment of secondary and exploratory endpoints

**Each original treatment combination** (defined as the treatment combination that was used by the patient at the very start of retrospective observation period, i.e. first recorded treatment combination in the study) will be tabulated by the below listed parameters using the generic table format below (see example tables: Table 10, Table 11, Table 12 and Table 6):

- Demographic data;
- Disease activity at Visits 1, 2, 3 (Mayo, Harvey-Bradshaw indices);
- Disease status assessed by investigator at Visits 1, 2, 3;
- Frequency (percentage) of clinical, endoscopic and histologic remission at Visits 1, 2, 3 and retrospective period of observation;
- Extent of lesion at Visits 1, 2, 3;
- Systemic (extraintestinal) manifestations at Visits 1, 2, 3;
- Total number, duration and severity of disease exacerbations by Visit 1, 2 and 3;
- Total number, type and duration of disease complications by Visit 1, 2 and 3;
- Laboratory and instrumental assessments at Visits 1, 2, 3;
- Percentage of patient with surgical treatment by Visits 1, 2, 3 grouped by:
  - Indication;
  - Surgery type;
  - Presence of complications.
- Number of surgeries by Visits 1, 2, 3;

Protocol ID	MACS-2017-102279	STATISTICAL ANALYSIS PLAN	Page 25 of 41	
IP	N/A		Date	30.12.2021
ID	MACS-2017-102279_SAP		Version	v1.2 final

- Percentage of patients with at least one episode of failure or biological or/and non-biological therapy (e.g., dose escalation of biologics, switching to another therapy, IBD-related surgery, medication augmentation) by Visits 1, 2 and 3;
- Separately for patients who achieved / not achieved T2T treatment goals (based on the clinical assessment of IBD) by Visits 1, 2 and 3:
  - Presence of therapeutic de-escalation;
  - Presence of therapeutic escalation;
  - Continuation of therapy without any changes.
- Healthcare resources utilization:
  - Hospitalizations due to complications;
  - IBD-related surgeries;
  - Percentage of patients that used healthcare resources;
- Only for biological therapy - percentage (by Visits 1, 2, 3) of patients with:
  - Positive test results for TB before the start of biological therapy;
  - Active TB before the start of biological therapy;
- Percentage of patients by Visits 1, 2, 3 with:
  - Reactivation of TB;
  - New occurrence of TB.

**The same information will be provided for the treatment pattern (if the corresponding treatment pattern will be large enough to make statistical inferences).**

As treatment pattern change over time, patterns will be assessed for certain time points and the change of patterns will be tracked throughout the study (see also example Table 8):

- Retrospective treatment pattern (change assessment for every 6 months of the 2-year treatment interval);
- Treatment pattern between the date of enrollment and 6 months;
- Treatment pattern between 6 and 12 months.

Accordingly, for each above-mentioned period, each pattern will be assessed for the history of changes (see example Table 8):

- Presence of dose modifications;
- Presence of discontinuations / treatment changes;
- Presence of flares (during the course of treatment);
- Add-on therapy.

Protocol ID	MACS-2017-102279	STATISTICAL ANALYSIS PLAN	Page 26 of 41	
IP	N/A		Date	30.12.2021
ID	MACS-2017-102279_SAP		Version	v1.2 final

In order to track the history of transition of subject “states” (i.e. treatment using the certain pattern from the list above), in addition to the descriptive 6-monthly data, transition state (Sankey) diagrams will be built (see Figure 2 for mock example) to visualize the subject journey across patterns as well as trends of pattern change over time.

Treat-to-target (T2T) success will be assessed (in this SAP) using EDC data, based on the definition of failure to meet T2T goals (*lack of clinical and endoscopic remission based on investigator's feedback and objective methods of evaluation*). Overall T2T success or failure will be analyzed separately from this SAP using Investigator Survey data.

T2T treatment factors will be assessed by Visits 1, 2 and 3 and will be grouped by:

- Clinician-related factors:
  - Frequency and methods of assessment of UC/CD disease activity;
- Patient-related factors:
  - Demographic data;
  - Time frame between the date of first symptom(s) and the date of IBD diagnosis;
  - Smoking status;
- Disease-related factors:
  - Age of disease onset;
  - Location of disease;
  - Clinical course;
  - Disease severity;
  - Presence of intestinal and systemic (extraintestinal) manifestations;
  - Presence of complications;
  - Surgical treatment.

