6.2 Study outcomes

The following outcomes will be evaluated in this study separately for UC and CD patients, within each group for subgroups of patients on biologic and non-biological therapy. Study outcomes will be analysed separately for the patients achieved and not achieved clinical remission during the study.

Primary outcomes:

- Distribution of treatment patterns used in patients with moderate to severe UC and with moderate to severe CD treated with biologics. Treatment patterns will be evaluated within 2 years before enrolment – retrospective data and one year after enrolment- prospective data and will include name and type of drug (original product or biosimilar) and treatment regimen including modifications.
- Distribution of treatment patterns used in patients with moderate to severe UC and with moderate to severe CD treated with non-biological treatment. Treatment patterns will be evaluated within 2 years before enrolment – retrospective data and one year after enrolment- prospective data and will include treatment regimen including modifications.

Secondary outcomes:

- Distribution of socio-demographic variables in patients with moderate to severe UC/ CD treated with biologics or/and non-biological treatment.
- Distribution of clinical variables in patients with moderate to severe UC/ CD treated with biologics or/and non-biological treatment. Clinical characteristics include family history of IBD, smoking habits (no smoker, ex-smoker and current smoker), medical history comorbidities, disease characteristics (age of disease onset, location of disease, clinical course, disease severity, intestinal and systemic (extraintestinal) manifestations, complications in history and during the study observational period, etc.).
- Description of methods used for documentation of disease activity in routine practice (incl. clinical, endoscopic, lab, histological), and frequency of objective CD/UC disease activity assessment using different methods.
- Percentage of moderate to severe IBD patients achieved clinical and combined clinical and endoscopic remission (based on T2T definitions).
- Percentage of patients with moderate to severe IBD with at least one episode of failure of biological therapy or/and non-biological therapy (e.g., dose escalation of biologics, switching to another therapy, IBD-related surgery, medication augmentation).

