15.2.2. Statistical analysis methods

All data from patients enrolled in this study will be analyzed. Information on CD and UC patients will be presented separately. Also, analysis will be performed separately by therapy subgroups (patients receiving non-biological therapy and patients receiving biological therapy). Due to complexity of treatment regimen a manual review can be used to define treatment subgroup for each patient.

A descriptive analysis approach will be used to analyze the data and the study outcomes for the different study subgroups.

Descriptive statistics will include summary tables (n, mean, median, standard deviation, minimum and maximum, lower and upper quartile for continuous variables and n, frequency and percentage for categorical values). Proportion will be assessed together with 95% confidence interval, if applicable. Cross tabulations will be used to present study outcomes by the corresponding subgroups, when required. Time to event will be described with Kaplan-Meier estimates. Median time to event will be presented together with the lower and upper quartiles. Baseline and retrospective data will be used to describe the patient population and will be tabulated separately.

The number and percentage of patients who have reached remission while in the study will be presented. Selected outcomes will be reported separately for those who have reached remission and those who haven't.

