15.4 Determination of Sample Size

The primary objective of this study is to obtain the accurate and comprehensive information regarding the treatment regimens used in patients with moderate to severe UC and CD flare within routine clinical practice in Russia, Belarus and Kazakhstan. For this purpose, sample size should be large enough to contain essential number of patients with different therapy options.

One of the key secondary objectives is to assess the percentage of Ulcerative Colitis (UC) and Crohn's Disease (CD) patients with at least one episode of failure of non-biological therapy with immunosuppressive agents or biological therapy registered within 12 months from the beginning of moderate to severe IBD flare. Based on literature data, up to 20-40% of IBD patients

experience failure of TNF antagonist therapy initially, and in 10-20% of patients per year loss of response is observed.

Assuming the percent of patients receiving biological therapy in the study population is 40%, about 40% proportion of CD patients [5, 6] and that 40-50% of the patients on biological therapy will have at least one episode of treatment failure during 12 months, enrolment of 2000 patients totally will be sufficient to estimate the proportion of patients on biological therapy with treatment failure during the 12 months of observation with acceptable precision in both UC and CD subgroups ($\pm 5.8\%$ for the smaller subgroup of CD patients and the assumed failure rate of 50%). The table below shows 95% confidence intervals for the estimated proportions of 40%, 50% and different sample size values. For other, more prevalent subgroups (CD patients on non-biological therapy, UC patients on each type of therapy) the proposed sample size will also allow to estimate proportion of patients with treatment failure with same or higher precision.

The total number of patients to be enrolled	The number of CD patients on biotherapy*	The number of CD patients in the analysis assuming 10% drop-out	Assumed failure rate of biotherapy**	
			40%	50%
2000	320	288	34.3-45.7%	44.2-55.8%
2500	400	360	34.9-45.1%	44.8-55.2%
3000	480	432	35.4-44.6%	45.3-54.7%
3500	560	504	35.7-44.3%	45.6-54.4%
4000	640	576	36.0-44.0%	45.9-54.1%
4500	720	648	36.2-43.8%	46.2-53.8%
5000	800	720	36.4-43.6%	46.3-53.7%

* Assuming the percent of patients receiving biotherapy is 40% among the study population. The precision (95% CI) is shown for the smaller subgroup of CD patients (approximately 40%).

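### SAP 8.1.3 groups failure and remission up to Visit 3 by the first recorded treatment combination; no available SAP methods sentence carries out the protocol's biological/non-biological split or dates the class assignment

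*SAP*

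**What the plan says.** **Grouping in the SAP.** SAP 8.1.3 tabulates the secondary and exploratory outcomes by original treatment combination, "defined as the treatment combination that was used by the patient at the very start of retrospective observation period". Remission at Visits 1, 2 and 3 is in that list. So is failure, whose examples end "switching to another therapy, IBD-related surgery, medication augmentation) by Visits 1, 2 and 3". The same section repeats the information by treatment pattern if the pattern is large enough, and follows patterns over six-month periods. SAP 8.1.2 defines a pattern to include change over time, and SAP 8.1.4 gives each pattern a column, as Protocol 15.2.1 does.

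**Grouping in the protocol.** Protocol 6.2 asks for outcomes for UC and CD separately and "within each group for subgroups of patients on biologic and non-biological therapy". Protocol 15.2.2 repeats this: "analysis will be performed separately by therapy subgroups (patients receiving non-biological therapy and patients receiving biological therapy". On how patients are placed, it says only that "a manual review can be used to define treatment subgroup for each patient".

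**Sample size.** Protocol 15.4 takes 2000 patients as enough to estimate "the proportion of patients on biological therapy with treatment failure during the 12 months of observation" in both diseases, giving ±5.8% for CD at a 50% failure rate. It then claims the same or better precision elsewhere: "For other, more prevalent subgroups (CD patients on non-biological therapy, UC patients on each type of therapy". The same section, and SAP 8.2, also describe the failure outcome as "registered within 12 months from the beginning of moderate to severe IBD flare".

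**The concern.** The grouping variable is fixed at the start of the two-year retrospective window, while the outcomes run to Visit 3. Take a patient on an immunosuppressant at the start of that window who begins a biologic a year later and enrols on it. In the original-combination table, this patient's Visit 2 and Visit 3 results sit under the immunosuppressant. Someone reading that table for outcomes on current therapy would credit the biologic's remission, or its failure, to the earlier drug.

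The protocol's split by therapy class would avoid this if class were fixed at a date suited to the prospective year. No date is given, so two analysts could form different biological groups from the same records, for example by class at first record, class at Visit 1, or any biologic use. The estimate on which enrolment was justified is the one exposed to this choice.

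**Working it through.** **1. The plan's own figure.** Inputs from Protocol 15.4: N = 2000, 40% CD, 40% on biologics, 10% drop-out, 50% failure.

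- n = 2000 × 0.40 × 0.40 × 0.90 = 288
- half-width = 1.96 × √(0.5 × 0.5 / 288) = 5.8 points, i.e. 44.2–55.8%

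This matches the protocol. The Clopper-Pearson interval planned for binary data gives 44.1–55.9% at 144/288.

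**2. The other three cells.** Same formula, assuming the 40% biologic share holds in both diseases:

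- CD non-biological: 2000 × 0.4 × 0.6 × 0.9 = 432, ±4.7 points
- UC biological: 2000 × 0.6 × 0.4 × 0.9 = 432, ±4.7 points
- UC non-biological: 2000 × 0.6 × 0.6 × 0.9 = 648, ±3.85 points

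The precision claim in 15.4 is therefore sound, provided the four pooled cells are what is reported.

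**3. Age of the label.** The retrospective window is 24 months and observation is 12 months, so the original combination can be 24 + 12 = 36 months old at Visit 3. The sized estimate covers 12 months.

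**4. What the grouping date could do to the sized cell.** The documents do not say how many of the 288 were already on a biologic at first record. The shares below are assumptions. They take all 432 CD non-biological patients to have started on non-biological therapy.

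| Assumed share already on a biologic | CD patients left under biological combinations | Half-width at 50% | Filed under non-biological combinations | Their share of that group |
|---|---|---|---|---|
| 75% | 216 | ±6.7 | 72 | 72/504 = 14% |
| 50% | 144 | ±8.2 | 144 | 144/576 = 25% |
| 25% | 72 | ±11.5 | 216 | 216/648 = 33% |

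The half-widths suppose that all biological combinations are added together. As written, 8.1.3 uses one group per combination, and those sizes are not given.

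**5. Search for the pooled split in the SAP text.**

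- SAP 7.1 splits by treatment type, but for safety outcomes only.
- SAP 7.4 lists patients without biological therapy, with no assignment date, and 8.1.4 makes division by those subgroups optional.
- SAP 3 states general compliance with the protocol but gives no columns, date or class rule.

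**6. The two failure windows (secondary).** For a flare that began F months before Visit 1, the first 12 months of the flare share max(0, 12 − F) months with the observation year: 12 at F = 0, 6 at F = 6, and none from F = 12 to F = 24. Inclusion criterion 3 admits flares up to two years back.

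**The case against.** The strongest reply is that the pooled analysis is already committed in Protocol 15.2.2, that the SAP declares compliance with the protocol, and that 8.1.3 refers to example tables for its layout. Those tables were not available for this review. A reader might infer that the SAP contains no pooled columns anywhere; that cannot be concluded. What stands is narrower: the written methods do not state the split for failure and remission, and the first-record definition is explicit whatever the table shells show.

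A reader might also infer that the original combination is the only grouping, or that a pattern is just one fixed combination. Neither is right. Patterns include change over time, so a patient who moved to a biologic before Visit 1 has a different pattern from one who did not, and the column-per-pattern layout is the protocol's own. But pattern tables depend on size and do not amount to a biological and a non-biological total.

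A third tempting reading is that JAK inhibitors are classified in two conflicting ways. SAP 7.4 places tofacitinib under first-line biological therapy. SAP 8.1.2 gives JAK inhibitors their own rows, but it does the same for TNF inhibitors and vedolizumab; a separate row is not a different class.

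Finally, the study is descriptive and the original-combination tables are openly defined, which limits the harm. Class at Visit 1 is one defensible convention among several. Both remarks are fair, but neither supplies the missing date.

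**Conclusion.** The point holds in this form and should be fixed; confidence is medium. By its own definition, SAP 8.1.3 places the prospective outcomes of patients who changed class before Visit 1 under their earlier therapy. The available SAP methods text does not carry out the protocol's class split for failure and remission, and neither document dates the assignment. The cell at stake is the one used for sizing: 288 CD patients on biologics, ±5.8 points. That figure is correct and needs no change.

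How many patients are affected is unknown. The 25–75% range in the working is an illustration, not an estimate. The conclusion about columns is limited to the text that could be read. The mismatch between the two failure windows is a secondary matter, found in the sample-size rationale; the outcome as listed in Protocol 6.2 names no window.

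**What to change.** Add to SAP 8.1.3 a main table of Visit 2 and Visit 3 failure and remission by therapy class at Visit 1 (biological, non-biological) within UC and within CD. Report 12-month failure counted from Visit 1 as a percentage with the planned Clopper-Pearson interval. Write down the class rule that any manual review must apply, including whether JAK inhibitors follow the SAP 7.4 placement or another stated one. Keep the original-combination tables as supplementary output, labelled as grouped by therapy at first record. If the example tables already hold pooled columns, the SAP need only say so and add the date and the rule.

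Separately, reconcile the two failure windows in Protocol 15.4 and SAP 8.2.

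The cost is SAP wording and one more table set. No new data are needed: Protocol 12.3 collects treatment at the baseline visit, and Protocol 12.6.1 collects treatment start and end dates. The downside is that patients who switch after Visit 1 stay under their Visit 1 class; the planned six-month pattern tables and Sankey diagrams show those moves.

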#### 8.1.4 Data tabulation principles

All data will be presented descriptively for each defined treatment pattern and can be further divided into subgroups depending on the presence of certain factors of interest in data (see section 7.4).

All summary tables will be structured with a column for each pattern in the defined order and will be annotated with the total population size relevant to that pattern, including any missing observations relevant for the particular table.

#### 8.1.5 Safety data analysis

Collection of safety data starts with the signing of ICF for this study, so, there will be no safety data available for the retrospective part of the study.

Protocol ID	MACS-2017-102279	STATISTICAL ANALYSIS PLAN	Page 27 of 41	
IP	N/A		Date	30.12.2021
ID	MACS-2017-102279_SAP		Version	v1.2 final

Safety data will be presented for the population of all patients enrolled as well as for each defined treatment combination (or pattern, if applicable) separately. Data will be presented as total counts as well as distribution by SOC at Visits 1, 2 and 3:

- Overall frequency of all AEs;
- Frequency of all AEs that led to treatment discontinuation / treatment change regardless of their relation to a particular medication;
- Frequency of SAEs;
- Frequency of all SAEs that led to treatment discontinuation / treatment change regardless of their relation to a particular medication;
- Frequency of ADRs;
- Frequency of SADRs;
- Frequency of pregnancy cases.

Additionally, all AEs/SAEs and ADRs/SADRs will be tabulated according to their relation to a particular medication (see example Table 17), separate tables will be generated for each medication being a monotherapy and in treatment combination.

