11.1 Inclusion Criteria

Every eligible patient at participating investigational sites must meet the following criteria:

Inclusion criteria:

1. Male and female patients 18 years or older by the time of enrolment
2. Confirmed diagnosis of Crohn's disease or ulcerative colitis for at least 2 years prior to enrolment in the study.
3. The presence of a moderate to severe IBD flare at the time of enrolment or in patient anamnesis within 2 years before enrollment treated with steroids or/ and immunosuppressive agents or/ and biologic therapy. IBD flare(s) must be confirmed in the source documentation.
4. Current treatment with steroids or/ and immunosuppressive agents or/ and 5-ASA or/ and biologic therapy
5. Written informed consent, signed before the participation in the study begins.

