12.6 Treatments to be documented in the study

12.6.1 IBD treatment

Due to non-interventional design of the study, the decision about particular IBD treatment strategy to the patient is taken by treating physician. All IBD medications are not provided by Sponsor.

Following medications for IBD treatment should be registered in eCRF; 5-ASA, immunosuppressive agents (including azathioprine (AZA), 6-mercaptopurine (6-MP), methotrexate (MTX), cyclosporine A), corticosteroids and biologics.

The following data should be documented for steroids:

- INN name;
- release form;
- Route of administration
- Indication
- start date;
- initial and maximum daily dose;
- funding source;
- dose, if continued / end date and the reason for modification/ discontinuation, if discontinued.

The following data should be documented for 5-ASA, immunosuppressive agents:

- INN name;
- release form;
- Route of administration
- Indication start date;
- daily dose;
- funding source;
- continued / end date and the reason for modification/discontinuation.

The following data should be documented for biologics:

- trade and INN name;
- Indication start date;
- treatment regimen (induction or supportive care);
- dosage regimen;
- Route of administration
- funding source;
- continued / end date and the reason for modification/discontinuation.

If a physician takes a decision to change something from the above it must be documented in the eCRF.

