13.1.2 Additional Points to Consider for AEs/ADRs

An untoward finding generally may:

- Indicate a new diagnosis or unexpected worsening of a pre-existing condition. (Intermittent events for pre-existing conditions underlying disease should not be considered AEs/ADRs.)
- Necessitate therapeutic intervention.
- Require an invasive diagnostic procedure.
- Require discontinuation or a change in dose of study medication or a concomitant medication.
- Be considered unfavorable by the investigator for any reason.

Diagnoses vs signs and symptoms:

- Each event should be recorded to represent a single diagnosis. Accompanying signs (including abnormal laboratory values or ECG findings) or symptoms should NOT be recorded as additional AEs/ADRs. If a diagnosis is unknown, sign(s) or symptom(s) should be recorded appropriately as an AE(s)/ADRs.

Laboratory values:

- Changes in laboratory values are only considered to be AEs/ADRs if they are judged to be clinically significant (i.e., if some action or intervention is required or if the investigator judges the change to be beyond the range of normal physiologic fluctuation). A laboratory re-test and/or continued monitoring of an abnormal value are not considered an intervention. In addition, repeated or additional noninvasive testing for verification, evaluation or monitoring of an abnormality is not considered an intervention.
- If abnormal laboratory values are the result of pathology for which there is an overall diagnosis (e.g., increased creatinine in renal failure), the diagnosis only should be reported appropriately as an AE/ADRs.

Pre-existing conditions:

- Pre-existing conditions (present at the time of signing of informed consent) are considered concurrent medical conditions and should NOT be recorded as AEs/ADRs. However, if the patient experiences a worsening or complication of such a concurrent condition, the worsening or complication should be recorded as an AE/ADRs (worsening or complication occurs after start of study medication). Investigators should ensure that the event term recorded captures the change in the condition (e.g., “worsening of...”).
- If a patient has a pre-existing episodic condition (e.g., asthma, epilepsy) any occurrence of an episode should only be captured as a AE/ADRs if the episodes become more frequent,

serious or severe in nature, that is, investigators should ensure that the AE/ADR term recorded captures the change in the condition from Baseline (e.g. “worsening of...”).

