13.2.3. Collection and reporting of AEs and ADRs

The following safety data should be reported by the investigator to the responsible CRO:

- adverse drug reactions on IBD treatments,
- adverse events on Entivyo® (vedolizimab) treatment,
- serious adverse events on IBD treatments (including Entivyo® (vedolizumab) treatment).

Start of AEs and ADRs collection: AEs/ADRs must be collected from the date after ICF signing. Routine collection of AEs/ADRs will continue until Final visit (Visit 3).

A physician must report all reportable AEs and ARDs on the special “AE reporting form” provided by the Sponsor. The physician should record only one AE per 1 “AE reporting form”. The physician has to record the diagnosis if available. If no diagnosis is available, the physician should record each sign and symptom as separate reports.

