## 7.2 ***Methods and timelines for the assessment of safety endpoints***

Start of AEs and ADRs collection: AEs/ADRs must be collected from the date after ICF signing. Routine collection of AEs/ADRs will continue until Final visit (Visit 3).

A physician must report all reportable AEs and ARDs on the special “AE reporting form” provided by the Sponsor. The physician should record only one AE per 1 “AE reporting form”. The physician has to record the diagnosis if available. If no diagnosis is available, the physician should record each sign and symptom as separate reports

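### Adverse-reaction tables pool drugs already running at consent with drugs begun after it, so treatment columns cover different parts of the risk period

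*SAP*

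**What the plan says.** **Collection window.** Protocol 13.2.3 states that "AEs/ADRs must be collected from the date after ICF signing". SAP 7.2 adds the end point: "Routine collection of AEs/ADRs will continue until Final visit (Visit 3"). Neither ties the window to the date a drug was started. SAP 8.1.5 draws the consequence for the two-year look-back: "so, there will be no safety data available for the retrospective part of the study".

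**Who enters.** Inclusion criterion 4 (Protocol 11.1) is "Current treatment with steroids or/ and immunosuppressive agents or/ and 5-ASA or/ and biologic therapy". There is no new-user restriction, and diagnosis must be at least 2 years old. The safety population (Protocol 15.1, SAP 8.6) is anyone with a dose of any IBD medicine after enrolment.

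**Events present at consent.** Protocol 13.1.2: "Pre-existing conditions (present at the time of signing of informed consent) are considered concurrent medical conditions and should NOT be recorded as AEs/ADRs". The same bullet goes on to require that a worsening or complication be recorded.

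**Tabulation.** SAP 8.1.5: "Safety data will be presented for the population of all patients enrolled as well as for each defined treatment combination", with further tables for each medication alone and in combination. SAP 8.1.4 gives summary tables one column per pattern. The safety outcome (Protocol 6.2, SAP 7.1) is patient incidence of ADRs and related SAEs over 12 months, by treatment type and by biologic-naive or prior-biologic history.

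**Data available on stopping.** Protocol 12.6.1 records, for steroids, "continued / end date and the reason for modification/ discontinuation", with equivalent fields for 5-ASA, immunosuppressants and biologics. Protocol 12.3 extends IBD treatment data to the previous two years.

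**The concern.** The window is fixed to the calendar of the study and not to the exposure. This is left truncation of harms among prevalent users, combined with a fixed right-hand cut-off.

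- **Drug running at consent:** reactions between first dose and consent are not collected as AEs. A patient who stopped the drug for a reaction before consent, and entered on something else, does not appear under it.
- **Drug begun after consent:** the early period is seen from first dose, but only as much of it as fits before Visit 3.

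Both kinds of course go into the same column. If reaction risk changes with time on drug, or if follow-up on drug differs, the column percentage depends on its share of starters and on when they started, as well as on the drug.

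At stake is the stated safety outcome, which is incidence by treatment type. SAP 4.2 also adds an objective on safety criteria in different subgroups, SAP 7.4 defines first-line subgroups by drug, and SAP 8.1.1 plans exploratory analyses of associations between treatment patterns and outcomes. Readers will compare these columns.

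**Working it through.** **No planned figure to reproduce.** The documents give no ADR rate, time on drug or share of starters. Their only numeric planning figure (Protocol 15.4) concerns treatment failure. The arithmetic below is therefore an illustration on stated assumptions.

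**Inputs**
- From the documents: window from consent to Visit 3, taken as 12 months.
- Assumed: monthly reaction rate b = 1% after the first 3 months on drug, and k × b during the first 3 months, with k from 1 to 4.
- Assumed: the same risk for every drug, no stopping within the window, and all ongoing users at least 3 months past drug start at consent.

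**Formulas**
- Ongoing users: 1 − exp(−12b) = 1 − exp(−0.12) = 11.3%.
- Starters, all at consent: 1 − exp(−(3kb + 9b)). At k = 3: 1 − exp(−0.18) = 16.5%.
- Starters spread evenly over the 12 months, so that time seen on drug is uniform on 0 to 12 months: 1 − (1/12) × [(1 − exp(−3kb))/(kb) + (exp(−3kb) − exp(−3kb − 9b))/b]. At k = 3: 1 − (2.869 + 7.866)/12 = 10.5%.

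| k | Ongoing | Starters, all at consent | Starters, spread evenly |
|---|---|---|---|
| 1 | 11.3% | 11.3% | 5.8% |
| 2 | 11.3% | 13.9% | 8.2% |
| 3 | 11.3% | 16.5% | 10.5% |
| 4 | 11.3% | 18.9% | 12.8% |

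**Effect on columns at k = 3.** Take two equally risky drugs with 60% and 10% starters (assumed shares).
- All starts at consent: 0.6 × 16.5 + 0.4 × 11.3 = 14.4%, against 0.1 × 16.5 + 0.9 × 11.3 = 11.8%. The gap is +2.6 points.
- Starts spread evenly: 0.6 × 10.54 + 0.4 × 11.31 = 10.8%, against 0.1 × 10.54 + 0.9 × 11.31 = 11.2%. The gap is −0.4 points.

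The sign changes with the timing of starts alone. Of the two forces, early high risk raises the starters' figure and the Visit 3 cut-off lowers it.

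**The extremes are not absolute.** At k = 3, a drug begun 1 month before consent still has 2 early months inside the window: 1 − exp(−(2 × 0.03 + 10 × 0.01)) = 14.8%. A drug begun at month 11 has about 1 month of capture: 1 − exp(−0.03) = 3.0%.

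**Does anything planned separate the two groups?** The biologic-naive or prior-biologic split is not time since start of the current drug, does not address non-biological drugs, and is not repeated in SAP 8.1.5. Protocol 15.2.4 gives general observational limitations and does not name prevalent use. No person-time rate or new-user subset is planned for harms. The example tables in SAP section 9 were not available for this review, so this rests on SAP 8.1.4 and 8.1.5.

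**The case against.** - **The study is descriptive.** SAP 8.3 plans no tests on tabulated data, and Protocol 15.2.4 states general limitations. That lowers the consequence. It does not make columns with different observation windows comparable, and incidence by treatment type is still the stated outcome.
- **SAP 8.1.5 presents combinations and medications separately.** This is so; the column layout comes from SAP 8.1.4. Separate tables still pool starters and ongoing users inside each one.
- **Direction.** A reader might infer that treatments with many new starters, such as vedolizumab (called new in Protocol 5.1) or the JAK inhibitors added in SAP v1.1, must look worse than established drugs. The documents do not support this. They give no starter shares, and the Visit 3 cut-off can reverse the sign.
- **Completeness.** A reader might also infer that early reactions are seen in full for new drugs and not at all for ongoing ones. Both are too strong, for the reasons shown in the two single-course examples.
- **Conditions at consent.** These are not lost altogether. Worsening is recordable as an AE or ADR, and the condition itself is kept and coded as a concurrent condition.
- **The retrospective sentence.** It is correct about AEs. Reasons for stopping are treatment data without seriousness or causality assessment, and for biologics SAP 6.1 already lists them in the primary endpoint. What remains is that the sentence is too absolute about what the look-back can show on harms.

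**Conclusion.** The point holds as a problem of comparability. The structural part follows from the text: one window for all, entry on current treatment, pooled tabulation, and no split by time since drug start. Differences between treatment columns can arise from the mix of starters and ongoing users with no difference in risk.

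The size and direction cannot be determined from the documents. In the illustration with k = 3, the starter-minus-ongoing difference is +5.2 points (16.5 − 11.3) if all start at consent and −0.8 points (10.5 − 11.3) if starts are spread evenly. It is nil with a flat rate and all starts at consent. With starts at consent, equal starter shares across columns would also remove the spurious difference. These figures rest wholly on the assumed rates and start times. No claim that a particular drug is favoured or penalised is supported.

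The change is worth making because drug start dates are already collected and the split needs no new data.

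**What to change.** In SAP 8.1.5:

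1. Tabulate ADRs and related SAEs per medication in two groups: (a) courses started after consent, as cumulative incidence from first dose with censoring at Visit 3; (b) courses ongoing at consent, as events per person-time on drug, with time since start shown.
2. Set treatments side by side only within (a) or only within (b).
3. Classify each drug course by its own start date, so that an add-on or a switch counts as a new course even when another drug in the combination is ongoing.
4. Reword the sentence on retrospective safety data to say that no AEs are collected retrospectively, but reasons for discontinuation are.
5. Where the recorded reason identifies an adverse reaction, add the cumulative incidence of stopping for that reason, for drugs started in the two retrospective years. Use a competing-risk (Aalen-Johansen) estimate, since Kaplan-Meier would censor stops for other reasons and overstate the proportion. Label it as limited to patients who later enrolled.

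The cost is SAP wording, a split of existing tables and one added table. Cells become smaller, especially in (a). JAK inhibitors are not named in the Protocol 12.6.1 field lists, so the availability of their start dates should be confirmed.
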